6.5 Secondary outcome 5. Clinical symptoms of neurological long COVID

Measure 5.1

Number of participants with clinical symptoms of neurological long COVID at 6 months post participation in trial.

We have several measures of neurological long COVID

Measure 5.1.1

The following symptoms were rated via telehealth or in person using a self-rated symptom assessment using a Likert scale (0-3: absent, mild, moderate, severe) for each symptom:

- Fatigue
- Malaise
- Daytime tiredness
- Impaired concentration
- Brain fog
- Sleep disturbance
- Forgetfulness
- Confusion
- Headache
- Dizziness
- Nausea
- Hypo/anosmia
- Hypo/ageusia
- Impaired walking
- Tingling feet or hands
- Burning feet or hands

- Numb feet or hands
- Impaired fine motor skills
- Muscle pain
- Epilepsy
- Anxiety
- Depression

In the first instance, an estimate will be calculated to compare the two randomised treatment arms, on each of the reported symptoms individually. The research question is: In individuals randomised to using heparin or placebo (both SARS-CoV-2 positive and negative at baseline) does heparin use vs placebo over 10 days reduce long covid symptoms at 6 months?

Estimand

Population: Household members (older than 5 years) enrolled in the study, regardless of SARS-CoV-2 infection status (all enrolled participants)

Treatment: Initially randomised intervention to unfractionated intranasal heparin 1400u each nostril (as heparin solution 5,000u/ml, 140microL/actuation, TWO actuations each nostril) THREE times daily via a plastic nasal inhalator device or saline control and any subsequent deviations to the per protocol use of the intervention over 10 days

Outcome: Ordinal Likert scale measurement of severity of each of the above symptoms at 6 months, with a 2 month window (i.e. including outcomes measured between 4 and 8 months)

Summary measure: The overall odds ratio will be reported with 95% confidence interval Potential intercurrent events:

Potential intercurrent events:

Index case in the household not taking study drug. This is defined as compliance <90% Participant (this household member) not taking study drug. This is defined as compliance <90% Either participant (this household member) or index case stop treatment due to adverse event Participant received an anti-viral

Strategy for handling intercurrent event:

All intercurrent events will be handled through the treatment policy strategy, which means that the intercurrent events will be ignored.

We will summarise the number of participants in each of the 4 categories of the Likert scale in each treatment arm. A mixed effects proportional odds logistic regression will be used to calculate the overall odds ratio, adjusted for the stratification variables and clustered on household. The assumption of proportional odds will be investigated. If it is violated, we will fit a multinomial regression and calculate an odds ratio for each category.

This analysis will also be repeated in the subgroup of participants who tested positive to SARS-CoV-2 infection at baseline.

The following subgroup analyses will be done with the symptom of fatigue as the outcome:

Age: Younger than 65 vs 65 and older

Pre-existing mental health problems: This will be measured by self-reported current comorbidities as mental health disorder (variable mhcat____18).

Previous SARS-CoV-2 infections: Any vs none

These subgroup analyses will be done by including an interaction term between the treatment arm and the subgroup in the mixed effects proportional odds logistic regression model described above. The p-value of the subgroup by arm interaction term will be assessed to determine whether there could be a subgroup effect, with the understanding that the analysis is probably underpowered.

Measure 5.1.2

Each symptom will be assigned a score of 0 if not present, 1 if mild, 2 if moderate and 3 if severe. These scores for each symptom will be added together to get the total neurological long COVID score, ranging from 0 to 66.

Estimand

Population: Household members (older than 5 years) enrolled in the study, regardless of SARS-CoV-2 infection status (all enrolled participants)

Treatment: Initially randomised intervention to unfractionated intranasal heparin 1400u each nostril (as heparin solution 5,000u/ml, 140microL/actuation, TWO actuations each nostril) THREE times daily via a plastic nasal inhalator device or saline control and any subsequent deviations to the per protocol use of the intervention over 10 days

Outcome: Continuous neurological long COVID score (described above) at 6 months, with a 2 month window (i.e. including outcomes measured between 4 and 8 months)

Summary measure: The mean difference between arms will be reported with 95% confidence interval **Potential intercurrent events**:

Index case in the household not taking study drug. This is defined as compliance <90% Participant (this household member) not taking study drug. This is defined as compliance <90% Either participant (this household member) or index case stop treatment due to adverse event Participant received an anti-viral

Strategy for handling intercurrent event:

All intercurrent events will be handled through the treatment policy strategy, which means that the intercurrent events will be ignored.

The same analysis as described for Measure 4.3 will be done.

This analysis will also be repeated in the subgroup of participants who had SARS-CoV-2 infection.

The following subgroup analyses will be done:

Age: Younger than 65 vs 65 and older

Pre-existing mental health problems: This will be measured by self-reported current comorbidities as mental health disorder (variable mhcat____18).

Previous SARS-CoV-2 infections: Any vs none

These subgroup analyses will be done by including an interaction term between the treatment arm and the subgroup in the model described for Measure 4.3. For example, using the Stata code mixed outcome i.arm##i.subgroup baseline_covariates || household:

The p-value of the subgroup by arm interaction term will be assessed to determine whether there could be a subgroup effect, with the understanding that the analysis is probably underpowered.

Measure 5.1.3

In addition to assessing whether treatment assignment was associated with neurological long COVID we want to investigate whether neurological long COVID outcomes were different for participants who tested positive for SARS-CoV-2 vs those who tested negative.

Estimand

Population: Household members (older than 5 years) enrolled in the study, regardless of SARS-CoV-2 infection status (all enrolled participants)

Exposures compared: Tested positive for SARS-CoV-2 any time during the study (baseline positive or positive during the trial) vs tested negative for SARS-CoV-2 at all time points

Outcome: Ordinal Likert scale measurement of severity of each of the symptoms listed in Measure 5.1.1. at 6 months, with a 2 month window (i.e. including outcomes measured between 4 and 8 months)

Summary measure: The overall odds ratio will be reported with 95% confidence interval

Potential intercurrent events: None

Strategy for handling intercurrent event: Not applicable

We will summarise the number of participants in each of the 4 categories of the Likert scale in each exposure group. A proportional odds logistic regression will be used to calculate the overall odds ratio, adjusted for the stratification variables and randomised arm and clustered on household. The assumption of proportional odds

will be investigated. If it is violated, we will fit a multinomial regression and calculate an odds ratio for each category.

Measure 5.1.4

In addition to assessing whether treatment assignment was associated with neurological long COVID we want to investigate whether neurological long COVID outcomes were different for participants who tested positive for SARS-CoV-2 vs those who tested negative. The research question is: Does testing positive for SARS-CoV-2 at baseline or during the 10 days of active treatment increase the severity of long COVID symptoms at 6 months?

Estimand

Population: Household members (older than 5 years) enrolled in the study, regardless of SARS-CoV-2 infection status (all enrolled participants)

Exposures compared: Tested positive for SARS-CoV-2 any time during the study (baseline positive or positive during the trial) vs tested negative for SARS-CoV-2 at all time points

Outcome: Continuous neurological long COVID score (described above) at 6 months, with a 2 month window (i.e. including outcomes measured between 4 and 8 months)

Summary measure: The mean difference between SARS-CoV-2 infected and uninfected participants will be reported with 95% confidence interval

Potential intercurrent events: None

Strategy for handling intercurrent event: Not applicable

The two exposures will be compared using mixed effects linear regression with neurological long COVID score as the outcome, adjusting for stratification factors (time from positive test to randomisation, whether the index case is a child < 5 years) randomised treatment arm and the defined baseline covariate set, with household as random effect to take the clustering by household into account.

The mean difference between the exposures will be calculated in Stata as follows using a mixed effects GLM with random intercepts:

mixed outcome i.infection_status i.arm baseline_covariates || household:

Measure 5.1.5

For participants over 16 years of age, cognition and mood were assessed using the harmonised procedures developed by the Neuro-COVID Neuropsychology International Task force. Included measures were:

- Cognitive screening using Telephone Montreal Cognitive Assessment (T-MoCA) Total Score
- Subjective cognitive complaints using Patient's assessment of Own Functioning Inventory (PAOFI) Total
 - o Memory
 - Language and communication
 - Use of hands
 - \circ Sensory-perception
 - o Higher-level cognitive and intellectual functions
 - Work/recreation
- Attention/working memory using the Wechsler Adult Intelligence Scale (WAIS) digit span
 - Digit Span Forward
 - $\,\circ\,$ Digit Span Backward
- Mood using the Depression, Anxiety and Stress Scales (DASS)
 - \circ Depression
 - o Anxiety
 - o Stress

For each of the tests and scales listed above we will calculate the following estimand:

Estimand

Population: Household members (older than 16 years) enrolled in the study, regardless of SARS-CoV-2 infection status (all enrolled participants)

Treatment: Initially randomised intervention to unfractionated intranasal heparin 1400u each nostril (as heparin solution 5,000u/ml, 140microL/actuation, TWO actuations each nostril) THREE times daily via a plastic nasal inhalator device or saline control and any subsequent deviations to the per protocol use of the intervention over 10 days

Outcome: Each continuous scale measuring cognition or mood as listed above at 6 months, with a 2 month window (i.e. including outcomes measured between 4 and 8 months)

Summary measure: The mean difference between arms will be reported with 95% confidence interval **Potential intercurrent events**:

Index case in the household not taking study drug. This is defined as compliance <90% Participant (this household member) not taking study drug. This is defined as compliance <90% Either participant (this household member) or index case stop treatment due to adverse event Participant received an anti-viral

Strategy for handling intercurrent event:

All intercurrent events will be handled through the treatment policy strategy, which means that the intercurrent events will be ignored.

The same analysis as described for Measure 4.3 will be done.

This analysis will also be repeated in the subgroup of participants who had SARS-CoV-2 infection.

Measure 5.1.6

In addition to assessing whether treatment assignment was associated with neurological long COVID we want to investigate whether neurological long COVID outcomes were different for participants who tested positive for SARS-CoC-2 vs those who tested negative.

For each of the scales listed in Measure 5.1.5 we will also calculate the following estimand:

Estimand

Population: Household members (older than 16 years) enrolled in the study, regardless of SARS-CoV-2 infection status (all enrolled participants)

Exposures compared: Tested positive for SARS-CoV-2 any time during the study (baseline positive or positive during the trial) vs tested negative for SARS-CoV-2 at all time points

Outcome: Each continuous scale measuring cognition or mood as listed in Section 5.1.5 at 6 months, with a 2 month window (i.e. including outcomes measured between 4 and 8 months)

Summary measure: The mean difference between SARS-CoV-2 infected and uninfected participants will be reported with 95% confidence interval

Potential intercurrent events: None

Strategy for handling intercurrent event: Not applicable

The same analysis as described in Measure 5.1.5 will be done.

Measure 5.2

Number of participants with clinical symptoms of neurological long COVID at 12 months post participation in trial.

The measures done at 6 months will be repeated at 12 months. The same analyses as described for 6 months (Measures 5.1.1 to 5.1.6) will be repeated at 12 months.

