3.9. Baseline covariate set

A set of covariates which will be included in models for all primary and secondary outcomes (unless specified otherwise) are: stratification factors (time from positive test to randomisation (binary)) and whether the index case is a child < 5 years(binary), participant age (continuous), inhaled steroid use at baseline (binary), days since symptom onset for index case at randomisation (continuous), whether there are children in the household (binary) and household size (continuous). This is referred to as the baseline covariate set.

Some of these covariates are correlated with each other and may also have sparse data in some of the cells, which may lead to convergence problems with the models. If that is the case, we will exclude some of the baseline covariate set until we can get a model that converges. We will first exclude the sparsest variables, and secondly exclude the variables most correlated with other variables.

We will also repeat each analysis with a model including only the two stratification variables.

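### The arm comparison of each long COVID symptom (Measure 5.1.1) leaves out participant age without a reason and so gives up a little power; adding age needs only a wording change

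*SAP*

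**What the plan says.** For the individual symptom ratings, SAP section 6.5, Measure 5.1.1, plans a proportional odds model with mixed effects, "adjusted for the stratification variables and clustered on household". It gives no reason for stopping at the two stratification variables (time from positive test to randomisation, and whether the index case is a child under 5).

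Section 3.9 sets the general rule: "A set of covariates which will be included in models for all primary and secondary outcomes (unless specified otherwise) are" the two strata, participant age, inhaled steroid use, days since the index case's symptom onset, children in the household, and household size. It expects sparse data and gives a step-down: "we will exclude some of the baseline covariate set until we can get a model that converges". It also says: "We will also repeat each analysis with a model including only the two stratification variables".

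Measure 5.1.2 adds up the same 22 ratings in the same population, arms and time window. Its model is given by reference: "The same analysis as described for Measure 4.3 will be done". Measure 4.3 in section 6.4 uses the full baseline covariate set.

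**The concern.** The same ratings in the same people are adjusted for age when summed but not when analysed one by one. Under section 3.9 the strata-only model is an extra analysis beside the main one. In Measure 5.1.1 it is the main model, so the planned pair of analyses becomes a single analysis.

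Participants analysed here are older than 5 years with no upper limit, and the items include forgetfulness, sleep disturbance, impaired walking and muscle pain. Age is plausibly related to such ratings, and the SAP itself chooses age as a subgroup factor for fatigue and for the sum score. Both strata are the same for everyone in a household, and neither directly balances participant age. What is at stake is some power, and some protection against a chance age difference between arms, in the 22 symptom comparisons, their 12-month repeats, the repeats in baseline positives, and the fatigue subgroup models on mental health and previous infection. The fatigue subgroup model by age already contains age, split at 65.

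**Working it through.** **1. The plan's own figures.** The SAP gives no sample size, power or precision for Measure 5.1.1. Its section 2.6 figures concern the primary outcome and serve here only to fix the trial size. With 85% vs 75%, two-sided alpha 0.05 and 80% power:

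n per arm = [1.96 × √(2 × 0.80 × 0.20) + 0.8416 × √(0.85 × 0.15 + 0.75 × 0.25)]² / 0.10² = 250.

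- Three contacts per household, intracluster correlation 0.2: 250 × 1.4 / 3 = 116.7, so 117 households per arm against 120 stated (close). Then 120 / 0.9 gives 134 per arm, 268 in total, as stated.
- Two contacts: 250 × 1.2 / 2 = 150; 150 / 0.9 gives 167 per arm, 334 in total, as stated.

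**2. Simulation of Measure 5.1.1 with and without age.**

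From the SAP: 268 households of four (1072 people), 1:1 by household, four-category outcome.

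Assumed, not in the SAP: conditional odds ratio 0.7 (log −0.357); household standard deviation 0.7 on the logit scale; within-household correlation of age 0.3; any-symptom prevalence about 40% or 5%; age effect 0 to 1.0 (log odds ratio per SD).

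Each setting had 400 runs. A proportional odds model was fitted with arm alone and with arm plus age. The strata were not simulated. The household effect was generated but not fitted, so the spread is the empirical SD of the estimates over runs. Then z = mean / SD, power = Φ(|z| − 1.96), and relative efficiency = (z with age / z without age)².

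| Prevalence | Age effect | Without age: mean (SD) | With age: mean (SD) | Relative efficiency | Power without → with |
|---|---|---|---|---|---|
| 40% | 0 | −0.323 (0.142) | −0.323 (0.142) | 1.00 | 0.62 → 0.62 |
| 40% | 0.3 | −0.325 (0.139) | −0.331 (0.139) | 1.04 | 0.65 → 0.66 |
| 40% | 0.6 | −0.317 (0.143) | −0.339 (0.148) | 1.06 | 0.60 → 0.63 |
| 40% | 1.0 | −0.286 (0.146) | −0.331 (0.149) | 1.27 | 0.50 → 0.60 |
| 5% | 0 | −0.373 (0.298) | −0.375 (0.299) | 1.00 | 0.24 → 0.24 |
| 5% | 0.3 | −0.354 (0.289) | −0.355 (0.290) | 1.00 | 0.23 → 0.23 |
| 5% | 0.6 | −0.355 (0.273) | −0.359 (0.275) | 1.02 | 0.25 → 0.26 |
| 5% | 1.0 | −0.330 (0.278) | −0.346 (0.278) | 1.10 | 0.22 → 0.24 |

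Example, fourth row: the printed z values are 1.97 and 2.22; (2.22 / 1.97)² = 1.27; Φ(0.01) = 0.50 and Φ(0.26) = 0.60.

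The SD does not fall when age is added. The mean log odds ratio moves away from zero, and the power comes from that. With an age effect of 0, adding age costs nothing visible.

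A smaller simulation (800 people, log odds ratio −0.4, no household effect, 150 runs) agrees in direction: relative efficiency 1.01, 1.05 and 1.07 for age effects of 0.3, 0.5 and 0.8.

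**3. Chance imbalance in age.** With 536 people per arm in households of four and an age correlation of 0.3, the design effect for mean age is 1 + 3 × 0.3 = 1.9. The arm difference in mean age then has standard error √(2 × 1.9 / 536) = 0.084 SD, against √(2 / 536) = 0.061 SD under individual randomisation. At an age effect of 0.6, an imbalance of 0.084 SD moves the unadjusted log odds ratio by roughly 0.6 × 0.084 = 0.05.

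**The case against.** The strongest case for leaving the text alone has four parts.

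- **The exception is allowed.** Section 3.9 says the default applies unless specified otherwise, and Measure 5.1.1 does specify otherwise. Measures 5.1.3 and 5.1.4 show the same split (strata and arm for the ordinal model, full set for the linear one), so it may be a deliberate choice by model type. This stands: a reader might infer a contradiction, but the text does not support one.
- **Precision is not lost.** A reader might infer that adding age would narrow the confidence intervals, as extra participants would. In a proportional odds model it does not, as the SDs above show. This stands; the gain is in power only.
- **The full set has a price.** There are 22 four-category models at each of two time points, some for rare items such as epilepsy, with a multinomial fallback if proportional odds fails. That fallback has three equations: 3 × 7 = 21 covariate slopes with the full set, 3 × 2 = 6 with strata only. Dropping covariates symptom by symptom would leave odds ratios that condition on different sets and compare poorly with one another. This stands against importing the whole section 3.9 set and its drop rule. It weighs little against adding age alone to every model (3 × 3 = 9 slopes).
- **Results may differ from Measure 5.1.2 anyway.** One reports odds ratios per symptom, the other a mean difference on a 0 to 66 score. This stands: a difference between them could not be put down to adjustment alone.

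Sparsity may be the unstated reason for the small model, but the SAP does not say so at Measure 5.1.1. The primary models, which section 5.1 also expects might fail to converge, still start from the full set and step down.

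**Conclusion.** The point holds as a minor, avoidable loss of power in a secondary analysis, together with an unexplained difference from Measure 5.1.2. It is not an error of inference. A reader might also infer bias or confounding; the arms are randomised and both strata are in the model, so the documents do not support that.

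The loss from omitting age is about 0 to 3 power points for a weak or moderate age effect (log odds ratio per SD up to 0.6), about 10 for a common symptom with a strong effect (1.0), and 0 to 2 for a rare symptom. These figures rest on the assumed odds ratio, prevalences, household variance and age correlation, on 400 runs per setting, and on all 1072 planned people being assessed. The SAP does not say how prognostic age is for any of these symptoms, so the true gain may be close to nothing.

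**What to change.** In Measure 5.1.1, adjust the main mixed effects proportional odds model for the two stratification variables plus participant age (continuous), clustered on household, with the same set for all 22 symptoms. Apply this at 12 months as well; the repeat in baseline positives and the fatigue subgroup models then follow. Keep the strata-only model as the repeat that section 3.9 already requires, and as the single fallback where a rare symptom's model does not converge. Mark in Table 17 and its repeats which symptoms used the fallback.

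The cost is SAP wording, with no new data. The downside is that the odds ratio becomes conditional on age as well as on the strata, and a few rare-symptom models (epilepsy, for example) may have to fall back to strata only. The strata-only repeat still gives readers one uniform set across all symptoms.

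### Pre-existing mental health disorder is collected but left out of the main long COVID models; this matters most in the non-randomised infected-versus-uninfected comparisons (Measures 5.1.3, 5.1.4 and 5.1.6)

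*SAP*

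**What the plan says.** All references are to the SAP; Measures 5.1.1 to 5.1.6 stand in Section 6.5.

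- **Outcomes.** Measure 5.1.1 takes 22 symptoms, among them fatigue, anxiety and depression: "The following symptoms were rated via telehealth or in person using a self-rated symptom assessment using a Likert scale (0-3: absent, mild, moderate, severe"). The outcome is the "Ordinal Likert scale measurement of severity of each of the above symptoms at 6 months". Measure 5.1.2 adds the items into a "total neurological long COVID score, ranging from 0 to 66". Measure 5.1.5 adds cognitive scales and "Mood using the Depression, Anxiety and Stress Scales (DASS"), taken as values at 6 months.
- **Population.** Participants count "regardless of SARS-CoV-2 infection status (all enrolled participants"), older than 5 years (older than 16 for 5.1.5 and 5.1.6).
- **Arm models.** The 5.1.1 model will "calculate the overall odds ratio, adjusted for the stratification variables and clustered on household". Measures 5.1.2 and 5.1.5 use the Measure 4.3 linear mixed model with the baseline covariate set of Section 3.9. Besides the stratification factors, age, children in the household and household size, that set contains "inhaled steroid use at baseline (binary), days since symptom onset for index case at randomisation (continuous"). It has no mental health or comorbidity term.
- **Infection-status models.** Measure 5.1.3 adjusts for the stratification variables and arm, and 5.1.4 for the baseline set and arm. Measure 5.1.6 refers back to 5.1.5, and so to the baseline set.
- **Use of the mental health variable.** "Pre-existing mental health problems: This will be measured by self-reported current comorbidities as mental health disorder" appears as a subgroup for fatigue under 5.1.1 and for the total score under 5.1.2. In both, the arm-by-subgroup interaction p-value is what is assessed.
- **12 months.** Measure 5.2 repeats all of this.

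**The concern.** By naming pre-existing mental health disorder as a subgroup, the SAP treats it as relevant to these outcomes. Yet it is not a covariate where its link to the outcome is most direct: the anxiety and depression items, the total score that contains them, and the DASS.

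Most is at stake in the comparisons of infected with never-infected participants. Measure 5.1.4 asks whether infection increases the severity of symptoms, which is a causal question, and infection status is not randomised. If people with a disorder are more or less likely to be in the infected group, their higher scores are credited to, or masked from, infection. Neither adjustment set addresses this.

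In the randomised arms the stake is smaller: lost precision and an uncorrected chance imbalance. Section 4.2 lists no mental health or comorbidity variable among the baseline characteristics, so the planned tables would not show such an imbalance either.

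**Working it through.** **Figures in the plan.** The score range reproduces: 22 items × 3 = 66. The SAP gives no SD, prevalence, correlation or power for any long COVID outcome, so the sizes below rest on stated assumptions.

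**1. Where the variable enters**

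| Measure | Contrast | Adjustment in main model | Mental health term |
|---|---|---|---|
| 5.1.1 | arms, ordinal | stratification variables | only in the fatigue subgroup model |
| 5.1.2 | arms, linear | baseline set | only in the subgroup model |
| 5.1.3 | infection, ordinal | stratification variables, arm | none |
| 5.1.4 | infection, linear | baseline set, arm | none |
| 5.1.5 | arms, linear | baseline set | none in the text |
| 5.1.6 | infection, linear | as 5.1.5 | none in the text |

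The subgroup models contain the variable's main effect. With an interaction present, however, the arm coefficient is the effect in one subgroup, so these models do not supply the main estimate.

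**2. Infection-status comparisons, linear scores.** If the disorder shifts the score by d SD and its prevalence differs by Δ between infected and uninfected, omitting it shifts the difference by about d × Δ. With d assumed 0.5-1.0, each 5 percentage points of Δ gives 0.5 × 0.05 = 0.025 to 1.0 × 0.05 = 0.05 SD. The SAP does not give Δ, so neither size nor direction can be fixed.

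**3. Arm comparisons, linear models.** For a binary covariate with prevalence p and shift d in within-group SDs:

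R² = p(1−p)d² / (1 + p(1−p)d²); SE ratio = √(1−R²); equivalent sample size ratio = 1/(1−R²).

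| p | d | p(1−p)d² | R² | SE ratio | Size ratio |
|---|---|---|---|---|---|
| 0.1 | 0.5 | 0.0225 | 0.022 | 0.989 | 1.02 |
| 0.2 | 0.8 | 0.1024 | 0.093 | 0.952 | 1.10 |
| 0.3 | 1.0 | 0.2100 | 0.174 | 0.909 | 1.21 |

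The SE therefore falls by 1-9%. As a detectable difference, take 536 persons per arm (Section 2.6), all followed, in households of 4, and assume that the ICC of 0.2 used for the primary outcome also applies. The design effect is 1 + 3 × 0.2 = 1.6 and the effective size 536/1.6 = 335. At 80% power and two-sided 0.05, (1.960 + 0.842) × √(2/335) = 0.216 SD. With the covariate this becomes 0.214 to 0.197 SD. Losses to follow-up, and the age limit in 5.1.5, would make all of these larger.

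**4. Chance imbalance.** At p = 0.2, the SE of the difference in prevalence between arms is √(2 × 0.16/536) = 0.024 without clustering and √(2 × 0.16/335) = 0.031 with design effect 1.6. The 95% limits are ±4.8 and ±6.1 percentage points.

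**5. Measure 5.1.1 behaves differently.** Treat one symptom as binary, present in 50-80% of the 20% with a disorder and in 20% of the others, with no treatment effect.

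- Overall proportion: 0.8 × 0.2 + 0.2 × 0.5 = 0.26, or 0.8 × 0.2 + 0.2 × 0.8 = 0.32.
- Unadjusted information per person: 0.26 × 0.74 = 0.192, or 0.32 × 0.68 = 0.218.
- Adjusted: 0.8 × 0.16 + 0.2 × 0.25 = 0.178, or 0.8 × 0.16 + 0.2 × 0.16 = 0.160.
- Ratio of SEs of the log odds ratio: √(0.192/0.178) = 1.04, or √(0.218/0.160) = 1.17.

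Adjustment thus raises this SE by about 4-17%. In exchange, the conditional odds ratio lies further from 1: in the same setting a conditional 0.70 corresponds to an unadjusted 0.72-0.77.

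**The case against.** Several objections are sound.

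- **Randomisation.** A reader might infer that the arm comparisons are biased. The documents do not support that: households are randomised 1:1 (Section 2.5), so the arm estimates are valid without the covariate. The precision gain is modest and rests on assumed inputs.
- **Scope of the SE figure.** It would be wrong to apply the 1-9% to every long COVID comparison. It does not apply to 5.1.1, as step 5 shows, and little gain is to be expected for digit span.
- **Not wholly unused.** The variable is in two subgroup models. Table 24 also calls for Table 22, the 5.1.5 arm comparison, to be repeated by subgroup. That table is labelled 5.1.6 and the text plans no such analysis, but the variable cannot be called absent everywhere for those scales.
- **What the ratings measure.** A reader might infer that the outcomes consist largely of long-standing mental illness. The SAP gives no prevalence, and many of the 22 items are sensory, motor or somatic. The SAP states no rule on new onset, but the protocol, not shown, may word the interview that way. Including everyone is the question Section 6.5 states, and the SAP also repeats analyses in infected participants.
- **Covariates already used.** Age is in the baseline set and may relate to cognition.
- **Convergence.** Sections 3.9 and 5.1 warn of sparse covariates. This is a real but small cost, since Section 3.9 already has a rule for dropping them.

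None of this answers the confounding point in 5.1.3, 5.1.4 and 5.1.6.

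**Conclusion.** The omission is real. It is a worthwhile improvement to secondary analyses, not an error that invalidates them.

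It weighs most in 5.1.3, 5.1.4 and 5.1.6 and their 12-month repeats. There, a variable that the SAP itself considers relevant is a possible confounder and is not adjusted for. The confounding is possible, not shown: it requires that prevalence differ by infection status, which the SAP does not report.

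In the arm comparisons there is no bias in expectation. For the linear models (the 0-66 score and the mood scales) the gain is an SE about 1-9% smaller, plus correction of chance imbalance. This assumes prevalence of 10-30%, a shift of 0.5-1.0 SD, and that `mhcat____18` was recorded before study drug was dispensed, as the word pre-existing implies.

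**What to change.** In SAP Section 6.5, prespecify `mhcat____18` as a covariate in:

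1. the infection-status models of Measures 5.1.3, 5.1.4 and 5.1.6;
2. the main linear arm models of Measures 5.1.2 and 5.1.5;
3. the ordinal arm models of Measure 5.1.1, at least for anxiety, depression and fatigue, with a note that the odds ratio is then conditional on it;
4. the 12-month repeats under Measure 5.2.

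Make the term subject to the existing convergence rule in Section 3.9. Optionally, title the tables as current neurological symptoms at 6 or 12 months, because never-infected participants are included.

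The cost is one binary term in existing Stata commands and no new data, with a small convergence risk for rarely reported items.
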